Protocol A6791040

PHASE IV OPEN LABEL SINGLE GROUP ONE YEAR STUDY OF HOME SELF-INJECTION WITH SAYANA® PRESS IN ADULT WOMEN OF REPRODUCTIVE AGE- A PRAGMATIC CLINICAL TRIAL

Statistical Analysis Plan

(SAP)

Version: 1.1 (Amendment)

Author: PPD , Clinical Statistics, PPD , PP

Date: 31-AUG2018

TABLE OF CONTENTS

1. AMENDMENTS FROM PREVIOUS VERSION(S)	4
2. INTRODUCTION	4
2.1. Study Objectives	5
2.2. Study Design	5
2.3. Sample Size	6
3. ENDPOINTS AND BASELINE VARIABLES: DEFINITIONS AND CONVENTIONS	.6
3.1. Primary Endpoint(s)	6
3.2. Secondary Endpoint(s)	6
CCI	
3.4. Baseline Variables	7
3.5. Safety Endpoints	7
4. ANALYSIS SETS	8
4.1. Full Analysis Set	8
4.2. Per Protocol Analysis Set	8
4.3. Safety Analysis Set	8
4.4. Other Analysis Sets	8
5. GENERAL METHODOLOGY AND CONVENTIONS	8
5.1. Hypotheses and Decision Rules	8
5.2. General Methods	8
5.2.1. Analyses for Binary Correlated Data	8
5.2.2. Analyses for Binary Data	9
5.2.3. Analyses for Categorical Data	9
5.3. Methods to Manage Missing Data	9
6. ANALYSES AND SUMMARIES	9
6.1. Analysis of Primary Endpoint	9
6.2. Analysis of Secondary Endpoint(s)1	0
6.4. Correlation Analyses	1

6.5. Subset Analyses	11
6.6. Baseline and Other Summaries and Analyses	11
6.6.1. Baseline Summaries	11
6.6.2. Study Conduct and Subject Disposition	12
6.7. Safety Summaries and Analyses	12
6.7.1. Adverse Events	12
6.7.2. Vital Signs	13
6.7.3. Physical Examination	13
7. INTERIM ANALYSES	13
8. REFERENCES	14
9. APPENDICES	15

Amendment Number	Date	Section Changed	Summary of Changes
1	31August2018	6.1 Analysis of Primary Endpoint	 Added plans for a sensitivity analysis. A sensitivity analysis will be conducted for the primary endpoint; this analysis will exclude primary endpoint data for sites that required closure during the study due to Good Practice violations. Clarified definition of repeated attempts in a single visit.
	31August2018	6.3 Analysis of Other Endpoint	• Clarified that, endpoints will be summarized by visit and by who administered injection at clinic.
	31August2018	6.7.1. Adverse Events	• Clarify language regarding analysis, AEs will be summarized by injection method.
	30August2018	Appendix 2	Removal of Visit windows.

1. AMENDMENTS FROM PREVIOUS VERSION(S)

2. INTRODUCTION

Study A6791040 is a Phase IV Open Label Single Group one year Study of Home Self-Injection with Sayana[®] Press in adult women of reproductive age, to be run in the United Kingdom.

This study is intended to provide information on the use of Sayana Press by women who self-inject the product at home over a 1-year period as part of Post Marketing Commitment (PMC) required by MHRA.

The application for approval of self-injection with Sayana Press was primarily based on a 1-year investigator-initiated study (Study GA67815) that used Sayana (DMPA-SC in a pre-filled syringe) and a usability study that used Sayana Press (DMPA-SC in UnijectTM) in which participants (volunteers) performed simulated injections into an injection trainer and assessed the functionality or usability of the device and the instructions for use for the device. While the GA67815 study showed that women can perform independent (at home) self-injection when using the pre-filled syringe, the UnijectTM device is fundamentally different from the syringe and MHRA has identified a need for a post-approval study that shows that women can similarly self- inject successfully when using the UnijectTM device rather than a standard pre-filled syringe.

This SAP provides the detailed methodology for summary and statistical analyses of the data collected in study A6791040. This document may modify the plans outlined in the protocol; however, any major modifications of the primary endpoint definition or its analysis will also be reflected in a protocol amendment.

2.1. Study Objectives

Primary Objective:

• Determine the proportion of women who are able to self-inject Sayana Press successfully over a 1-year period.

Secondary Objective:

CCI				
I				
I				
i				

• Assess continuation rate for the method at 1 year.

2.2. Study Design

This is an open-label, single-arm, non-randomized, 1-year study to assess home self-administration of Sayana Press in women who desire long-acting reversible contraception (LARC), are interested to attempt DMPA self-injection at home and are judged by their HCP to be good candidates for self-injection.

Following training and a supervised initial self-injection at the clinic, study participants will self-inject Sayana Press in the home setting every 3 months (at Month 3, Month 6 and Month 9) and return for a final study visit at Month 12. Participants will attend 2 or 3 study visits at the clinic: a Screening/Baseline Visit or Screening and Baseline visit separately and a Final Visit. At Months 3, 6 and 9, participants will be asked to contact the clinic by phone after performing each scheduled home self-injection in order to confirm the date of injection and to report any AEs, and/or injection difficulties or problems with the device.

At the Month 12 Final Visit or premature discontinuation, subjects will be asked to complete the CCI and the HCP will also complete a CCI.

2.3. Sample Size

The primary endpoint for this study is the proportion of all attempted home self-injections that were successfully performed by the study participant at home and on schedule. This will be presented as mean percentage of self- injections that were successfully administered, along with a 95% confidence interval using a clustered binomial analysis approach.

The self-administration success rate in a 1-year IIR study (GA678151) using data from 56 subjects who each had up to 3 injections, was estimated to be 88.8%, with 95% confidence interval 83.1% to 92.7%. This was determined using the generalized estimating equation (GEE) model for clustered binomial data, and estimated the intra-class correlation (ICC) to be 0.043.

Using a GEE model for clustered binomial data, and assuming the ICC to be 0.05, then for 100 subjects, the half-width of the 95% confidence interval for different success rates is simulated to be the following:

Response rate	Half-width of 95% confidence interval		
85%	4.6%		
90%	3.8%		
95%	2.8%		

To allow for subjects who have never used Sayana previously, some subjects who may not be proficient at self-injection after the training and to allow for some subjects who may discontinue the study, approximately 160 subjects will be enrolled to provide a sample size of at least 100 women who will perform the required self-injections at home and complete the follow-up questionnaires.

3. ENDPOINTS AND BASELINE VARIABLES: DEFINITIONS AND CONVENTIONS

3.1. Primary Endpoint(s)

The primary endpoint will be the proportion of all attempted home self-injections that were successfully performed by the study participant at home (ie, not in the clinic under direct HCP supervision) and on schedule (13 week interval ± 1 week).

3.2. Secondary Endpoint(s)

• Continuation rate for method at 1 year.

3.4. Baseline Variables

No baseline covariates in the planned analysis.

3.5. Safety Endpoints

Adverse events (AEs), including unplanned pregnancy and persistent injection site reactions, premature discontinuations, concomitant medications, vital signs and laboratory parameter (urine pregnancy test).

4. ANALYSIS SETS

Data for all subjects will be assessed to determine if subjects meet the criteria for inclusion in each analysis population prior to unblinding and releasing the database and classifications will be documented per standard operating procedures.

4.1. Full Analysis Set

The Full Analysis Set (FAS) will be defined as subjects who enroll into the study. All summaries of efficacy parameters will be reported within the FAS population.

4.2. Per Protocol Analysis Set

No per protocol analysis set is planned for this study.

4.3. Safety Analysis Set

The safety population will be defined exactly the same as the FAS population above. The safety population will be used for all safety summaries.

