5.3.3. Administration

The product will be administered in accordance with the label.

Study participants will be taught how to self-administer Sayana Press by the investigator or study centre staff using the training materials used according to standard of care in their practice, which are based on the approved Instructions for Use (IFU) for Sayana Press (Appendix 2). If the subject is comfortable attempting the Baseline Visit self-injection, the first self-injection will be performed at the clinic under the supervision of the study centre staff. If the subject adequately performs the first self-injection, and the investigator approves the subject to continue in the study, based on the subject's proficiency exhibited during the first self-injection, the subject will be then provided with 3 Sayana Press delivery system packages to take home. Subjects will be also given a copy of the Sayana Press IFU and contact information for the clinic. Subjects may also be given a reminder card or other reminder tools at the discretion of the Investigator.

If a self-injection did not occur due to malfunction or damage to the Sayana Press injector, a replacement Sayana Press injector should be provided to the subject at an unscheduled visit to replace it and the subject should self-inject immediately upon returning home.

If a scheduled injection is been delayed beyond the protocol-specified window (scheduled injection date ± 1 week), the subject should be advised to contact the clinic and speak to a healthcare professional regarding the need to exclude pregnancy before any additional injections, advice regarding additional contraception, and also for the timing of the next injection. A pregnancy test should also be conducted prior to the next scheduled injection.

Details regarding subject self-injection issues and reasons for self-injection failure must be documented in the subject's primary source records.

Following self-injection, the used Sayana Press injector should be immediately disposed of into a suitable container in accordance with the local regulatory authority requirements or per instructions from the Investigator.

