7.1. Pregnancy Testing

Urine pregnancy test, with sensitivity of at least 25 mIU/mL, will be performed at Screening, before Sayana Press administration at the Baseline Visit, and at the Final Visit. A negative pregnancy result is required before the subject may receive the first Sayana Press injection. Pregnancy test will also be done in any instance when potential pregnancy is suspected, if the Sayana Press injection is not conducted per the required schedule and at the end of the study to confirm the subject has not become pregnant during the study. Pregnancy tests may also be repeated as per request of institutional review boards (IRBs)/ethics committees (ECs) or if required by local regulations. In the case of a positive confirmed pregnancy, the subject will be withdrawn from administration of the Sayana Press product and from the study.

If the subject fails to self-inject or report to clinic for an injection (supervised or administered by HCP) within the +/- 1 week treatment window, the subject should be advised to contact the clinic and speak to a healthcare professional regarding the need to exclude pregnancy before any additional injections, advice regarding additional contraception, and also for the timing of the next injection. She should be advised to have a pregnancy test conducted at home or at the clinic prior to administering her next Sayana Press injection. The study centre must be informed if the subject has a positive at home pregnancy test and report to the clinic immediately. An Exposure During Pregnancy Form must be completed and submitted to Pfizer within 24 hours of awareness. The subject should also use a barrier method of contraception as instructed by the study investigator until she administers the next injection or, in cases when the subject decides to discontinue Sayana Press altogether, until the new contraceptive regimen is established.

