8.2. Reporting Period

For SAEs, the active reporting period to Pfizer or its designated representative begins from the time that the subject provides informed consent, which is obtained prior to the subject's participation in the study, ie, prior to undergoing any study-related procedure and/or receiving investigational product, through and including 28 calendar days after the last administration of the investigational product. SAEs occurring to a subject after the active reporting period has ended should be reported to the sponsor if the investigator becomes aware of them; at a minimum, all SAEs that the investigator believes have at least a reasonable possibility of being related to investigational product are to be reported to the sponsor.

AEs (serious and non-serious) should be recorded on the case report form (CRF) from the time the subject has taken at least 1 dose of investigational product through the last subject visit.

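### The safety set is all enrolled women, but AEs go on the CRF only after a first dose, so any woman enrolled and never injected dilutes the AE percentages

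*SAP*

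**What the plan says.** SAP 4.1 says of the Full Analysis Set (FAS) that it "will be defined as subjects who enroll into the study". SAP 4.3 adds no condition: "The safety population will be defined exactly the same as the FAS population above". It then says "The safety population will be used for all safety summaries", and SAP 4.4 plans no other set. No analysis-set definition in the SAP requires that an injection was received.

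Protocol 8.2 says "AEs (serious and non-serious) should be recorded on the case report form (CRF) from the time the subject has taken at least 1 dose", and footnote h to the Schedule of Activities repeats the rule. The same section starts SAE reporting to the sponsor earlier, at informed consent.

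Protocol 5.3.3 introduces the first injection with a condition: "If the subject is comfortable attempting the Baseline Visit self-injection". SAP 6.6.2 plans to report how many women were enrolled and how many were treated, as separate counts.

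**The concern.** An AE percentage should have as its denominator the women in whom an AE could have been recorded. Here the two rules start at different points: a woman enters the denominator at enrolment, but her AEs reach the CRF only once she has had a dose. Between those points she can add to the denominator and not to the numerator.

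The rest of the SAP's safety section presupposes treatment. SAP 6.7.1 defines treatment-emergent events relative to a start of treatment, sets the AE timeframe from the last injection, and tabulates AEs by injection method. A woman who was never injected has none of these. SAP 6.6.2 also promises reasons for exclusion from the analysis populations, although SAP 4.1 and 4.3 as written exclude no enrolled woman.

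At stake is modest understatement of AE percentages. Protocol 1.2 presents the study as part of a post-authorisation safety study required by the regulator, so understatement is the less welcome direction of error.

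**Working it through.** The documents give no AE rate, no count of untreated women and no safety-set size, so there is no figure of the plan's own to reproduce.

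**Can a woman be enrolled and not injected?**
- Registration, training and the first injection are all Baseline Visit procedures (Protocol 6.2).
- The first injection depends on the woman being comfortable attempting it (Protocol 5.3.3).
- SAP 6.6.2 treats enrolled and treated as different counts.
- Neither document says whether enrolment means consent, registration, or approval to continue.

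The plan therefore allows such women but does not say how many to expect.

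**Inputs**
- N = 160 enrolled (Protocol 9.1, SAP 2.3).
- u = number enrolled and never injected. Not in the documents; assumed 0, 2, 8 and 16.
- r = AE rate among injected women. Not in the documents; assumed 20%, with 10% for comparison.

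**Formula**
- Women with a CRF-recorded AE = r × (N - u).
- Reported percentage = r × (N - u)/N = r × (1 - u/N).
- Relative understatement = u/N.

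**Results for N = 160**

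| u | factor | r = 20% reported as | r = 10% reported as | relative understatement |
|---|---|---|---|---|
| 0 | 160/160 = 1.0000 | 20.0% | 10.0% | 0% |
| 2 | 158/160 = 0.9875 | 19.75% | 9.88% | 1.25% |
| 8 | 152/160 = 0.9500 | 19.0% | 9.5% | 5.0% |
| 16 | 144/160 = 0.9000 | 18.0% | 9.0% | 10.0% |

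With the denominator restricted to the N - u injected women, the reported percentage equals r in every row.

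The plan allows for up to 160 - 100 = 60 non-completers. That is not a realistic value for u, because it includes women who stop after one or more injections.

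**The case against.** The strongest reply is that hardly any woman may be affected. Much of this stands.

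- **Non-approval after training.** A reader might infer that women who fail the proficiency check, for whom the 160 explicitly allows, are enrolled and untreated. The documents do not support that as the general case. Under Protocol 4.5 and 5.3.3, approval follows the first supervised attempt and concerns the later home injections, so a woman who is not approved has normally attempted a dose.
- **Positive baseline pregnancy test.** Protocol 7.1 says "A negative pregnancy result is required before the subject may receive the first Sayana Press injection", and a reader might count a woman stopped here as enrolled and untreated. But pregnancy is an exclusion criterion (Protocol 4.2), and Protocol 6.1 screens women, with a urine test, before enrolment. A positive test is more naturally an eligibility failure. Registration comes before the test in the Protocol 6.2 list, but that is a list of procedures for one visit and does not establish a sequence.
- **All safety percentages must fall.** A reader might infer that SAE percentages are necessarily diluted too. Protocol 8.2 has SAEs reported to the sponsor from consent, so a pre-dose SAE can reach the safety database. The documents do not say how it would enter the tables, so the claim is not established for SAEs.
- **A reader can correct it.** SAP 6.6.2 reports the treated count, so any dilution is visible and can be undone. The study is single-arm and descriptive (SAP 5.1), and no decision rule depends on an AE percentage.

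What remains is the conditional first injection in Protocol 5.3.3, which applies to women already selected as willing to self-inject at home, together with the undefined meaning of enrolment. That is enough to show that the stated denominator rule does not match the recording rule. It does not show that the mismatch will be large.

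**Conclusion.** The point holds as a mismatch between two written rules. Whenever an enrolled woman is never injected, the overall percentages of CRF-recorded AEs are understated by the fraction u/N. Under the assumed values, a 20% rate is reported as anything from 20.0% (u = 0) to 18.0% (u = 16 of 160). The values of u and the AE rate are illustrations and do not come from the documents. The true u depends on what the sponsor counts as enrolment, is probably small and may be zero, in which case no figure changes. The point does not extend to a firm claim about SAEs, and it does not touch the primary analysis. It is a minor correction.

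**What to change.** In the SAP:
- **4.3:** define the safety set as enrolled women who received at least one full or partial injection, and use it for all safety tables.
- **4.1:** keep the FAS for efficacy and disposition, and state which event counts as enrolment.
- **6.6.1:** state which set the baseline tables use. They now use the safety population, so they would change with it unless this is specified.
- **6.6.2:** show the number enrolled but not injected.
- **6.7:** list any SAE reported between consent and the first injection separately from the tables.

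The core change is one sentence, and the others are short clarifications. Trial conduct, data collection and the primary analysis are unaffected. The only visible consequence is that AE percentages may rise slightly.

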4.4. Other Analysis Sets

No other analysis sets are planned for this study.

5. GENERAL METHODOLOGY AND CONVENTIONS

5.1. Hypotheses and Decision Rules

As this is a single arm study, there will be no treatment comparisons, and all analyses will be descriptive.

5.2. General Methods

5.2.1. Analyses for Binary Correlated Data

The primary endpoint is the mean percent of self-injections that were successfully administered (ie, combined across visits). Each subject will have a maximum of 3 self-injections, each of which will be defined as a success or failure.

A success is defined as a home self-injection that was successfully performed by the study participant at home and on schedule (13 week interval ± 1 week). If the subject attempts but is unable to administer the self-injection at home and had it performed instead at the clinic, then these are classed as failures. If a subject discontinues from the study prior to attempting all 3 injections, or chooses not to attempt the injection at home, but have it performed in the clinic, then only the injections that were attempted at home will be evaluated and included in the analysis.

These binary outcomes are correlated within the subject, and they will therefore be analyzed with a generalized estimating equation (GEE) model for clustered binomial data, using subject as the clustering variable, to provide a proportion along with 95% confidence interval.

5.2.2. Analyses for Binary Data

For dichotomous categorical variable (continuation rate and proportion of attempted home self- injections where subject returned to clinic for the injection), the number of subjects and proportion will be presented, as well as a 95% confidence interval (using normal approximation to binomial).

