2.2. Endpoints

Primary Endpoint

The primary endpoint will be the proportion of all attempted home self-injections that were successfully performed by the study participant at home (ie, not in the clinic under direct HCP supervision) and on schedule (13 week interval +/- 1 week). If a subject decides to discontinue Sayana Press as her contraceptive method, and therefore does not attempt 1 or more injections, these scheduled injections would not be included in the denominator for the primary endpoint.

Secondary Endpoint

• Continuation rate for method at 1 year.

- Ease of self-injection, based on Question 10 of Subject Questionnaire (including any post-baseline self-injections that were performed under HCP supervision, which would not have been included in the primary analysis);
- Usefulness and type of reminder techniques used, based on Questions 5 and 6 of Subject Questionnaire;
- Proportion of attempted home self- injections where subject returned to clinic for the injection (to be administered by the a HCP or under supervision of one);
- Evaluate end of study plasma concentration of MPA;
- Reasons for electively discontinuing self-injection of Sayana Press (where the subject elects to continue to receive DMPA administered by a HCP at the clinic), based on Question 17 of Subject Questionnaire;
- Reasons for electively discontinuing Sayana Press altogether, based on Question 18 of Subject Questionnaire;
- Adverse Events (AEs), including unplanned pregnancy and persistent injection site reactions;
- Other information provided in Subject Questionnaire;
- HCP Questionnaire:
 - Percentage of suitable patients, based on Question 1;
 - Percentage of willing patients, based on Question 2;
 - Usefulness of training materials, based on Question 3;
 - Ease to teach a patient to self-inject, based on Question 4;
 - Overall experience/other information and input, based on Questions 5, 6, and 7

CCI		

Safety Analysis

Safety data, consisting of all adverse events, including unplanned pregnancies, persistent injection site reactions, SAEs, premature discontinuations, concomitant medications, vital signs, height and weight, and laboratory parameters, will be tabulated and listed according to Pfizer's standard reporting algorithms.

The study will be registered in the European Union (EU) in the EU Clinical Trials Register and in the United States in the ClinicalTrials.Gov registry, according to local requirements.

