6.1. Analysis of Primary Endpoint

The primary endpoint is the mean percent of home self-injections that were successfully administered (ie, combined across visits). Each subject will have a maximum of 3 home self-injections, each of which will be defined as a success or failure. A success is defined as a home self-injection that was successfully performed by the study participant at home and on schedule (13 week interval ± 1 week). If the subject attempts but is unable to administer the self-injection at home and had it performed instead at the clinic, then that attempted self-injection would be classified as a failure. If a subject discontinues from the study prior to attempting all 3 home self-injections, or chooses not to attempt an injection at home, but has it performed in the clinic, then only the injections that were attempted at home will be evaluated and included in the analysis; ie, all attempts are included in the denominator. When several home attempts occurred at a visit, the last attempt is counted at a visit.

These binary outcomes are correlated within the subject, and they will therefore be analyzed with a GEE model for clustered binomial data, using subject as the clustering variable. The GEE model for this single-group analysis will use the logit link and working correlation structure of independence. This GEE model will include only the intercept term and is used to obtain a 95% CI based on standard error estimates that take into account the correlation of binary observations within the patient; the point estimate and 95% CI for the intercept will be back-transformed (anti-logit transformation) to obtain the point estimate and 95% CI on the proportion scale. The proportion estimate and 95% CI will be subsequently multiplied by 100 to obtain results on the percent scale. Note that proportion estimate from the GEE model equals:

Proportion of attempted self-injections successfully administered at home= (total # of successful home self-injections) / (total # of home self-injection attempts).

A sensitivity analysis will be conducted for the primary endpoint; this analysis will exclude primary endpoint data for sites who required closure during study due to Good Clinical Practice violations.

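### SAP 5.2.2's normal-approximation interval for clinic returns after a home attempt will usually cover less than 95% and sits too low

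*SAP*

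**What the plan says.** Protocol 2.2 lists among its endpoints the "Proportion of attempted home self- injections where subject returned to clinic for the injection". SAP 5.2.2 puts this endpoint together with the continuation rate under one method for simple binary data: "the number of subjects and proportion will be presented, as well as a 95% confidence interval (using normal approximation to binomial"). It mentions no continuity correction, no alternative interval and no rule for a zero count.

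Three other places bear on how the figure will be formed:

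- **Relation to the primary endpoint.** Under SAP 5.2.1, if a woman tries at home, cannot do it and "had it performed instead at the clinic, then these are classed as failures". A clinic return after a home attempt is therefore one kind of primary-endpoint failure.
- **Unit and display.** The amendment log entry for Section 6.3 says that "endpoints will be summarized by visit and by who administered injection at clinic". For the primary endpoint, SAP 5.2.1 instead describes injections "successfully administered (ie, combined across visits"); 5.2.2 has no such wording. Section 6.3 itself is not in the public copy.
- **Correlation and repeat attempts.** For the primary endpoint, SAP 5.2.1 states: "These binary outcomes are correlated within the subject", and uses a GEE clustered on subject. SAP 6.1 adds: "When several home attempts occurred at a visit, the last attempt is counted at a visit".

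**The concern.** The usual normal-approximation interval takes the observed proportion plus or minus 1.96 estimated standard errors. When the event is rare, that standard error is estimated from a handful of events. A low count gives both a low estimate and an interval that is too short, so the interval tends to fall below the truth. Clinic returns are a subset of a failure rate that the plan's own source puts at about 11%, so this is the range to worry about.

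The visible text favours a by-visit figure. If the last-attempt rule of SAP 6.1 also applies, each woman then contributes one attempt per visit, there is no clustering, and the interval formula is the only fault. If a figure pooled over the three visits is also reported, two further points arise. The interval would ignore the within-subject correlation that 5.2.1 recognises for the same injections, and a count of women would not be the numerator of a proportion of injections.

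At stake is the figure that shows how often a woman who tried at home had to go to the clinic instead. The error runs in the reassuring direction, because it understates how high that rate could be.

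**Working it through.** **Inputs**

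- Women per visit: 100 to 160 (SAP 2.3: about 160 enrolled, at least 100 completing).
- Attempts per woman: at most 3 (SAP 5.2.1 and 6.1).
- Clinic-return rate p: not given in either document. **Assumed 2% to 11%.** The top is 100% − 88.8% = 11.2%, from the success rate in SAP 2.3; the 2% floor has no documentary source.
- ICC, for the pooled case only: 0.05, borrowed from the primary endpoint's planning assumption (SAP 2.3).

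The plan states no precision figure for this endpoint, so there is none to reproduce. The half-widths in SAP 2.3 belong to the primary endpoint.

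**Formulas**, with x returns among n women and p̂ = x/n:

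- Planned, read as the plain Wald form: p̂ ± 1.96 √(p̂(1 − p̂)/n).
- Wilson: [p̂ + z²/2n ± z √(p̂(1 − p̂)/n + z²/4n²)] / (1 + z²/n), z = 1.96.
- Exact: Clopper–Pearson.
- Coverage at true rate p: the sum of binomial(n, p) probabilities over every x whose interval contains p.

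**What the intervals look like at n = 100**

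- 3 returns: 0.03 ± 1.96 √(0.03 × 0.97/100) = 0.03 ± 0.033, that is −0.3% to 6.3%. Wilson gives 1.0% to 8.5%.
- 0 returns: 0% to 0%. The exact upper limit is 3.6%.
- The lower limit is negative for 1, 2 or 3 returns, at n = 100 and still at n = 160.
- Chance of seeing 0 to 3 returns at one visit: 86% if p = 2%, 65% if 3%, 26% if 5%, 4% if 8%.

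**One point in full: n = 100, p = 3%.** The planned interval contains 3% only for x = 2 to 8. With x = 1 the upper limit is 2.95%, just short. The chance of x = 0 or 1 is 0.97¹⁰⁰ + 100 × 0.03 × 0.97⁹⁹ = 0.048 + 0.147 = 0.195. The chance of x ≥ 9 is 0.003. Coverage is 1 − 0.195 − 0.003 = 80.2%, the minimum over the range.

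**Exact coverage over the range, in steps of 0.05 percentage points**

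| Interval | n | Rates | Min | Mean | Max | Rates with coverage below 95% |
|---|---|---|---|---|---|---|
| Planned | 100 | 2–11% | 80.2% | 91.3% | 95.3% | 98% |
| Planned | 160 | 2–11% | 82.6% | 92.4% | 95.5% | 97% |
| Planned | 100 | 5–11% | 87.5% | 92.2% | 95.3% | 97% |
| Planned | 160 | 5–11% | 89.8% | 93.2% | 95.5% | 96% |
| Wilson | 100 | 2–11% | 92.7% | 95.4% | 97.7% | 35% |
| Wilson | 160 | 2–11% | 93.0% | 95.3% | 97.7% | 42% |

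The exact interval at n = 100 never falls below 95.1% and averages 97.1%.

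**Direction of the misses, planned interval, averaged over 2–11%.** At n = 100 the true rate is above the upper limit 8.0% of the time and below the lower limit 0.7%. At n = 160 the figures are 6.7% and 0.9%. Nominal is 2.5% on each side.

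**Only if pooled over visits.** Beta-binomial simulation, 100 women × 3 attempts, 40,000 replicates:

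| p | Planned, ICC 0 | Planned, ICC 0.05 | GEE of SAP 6.1, ICC 0.05* |
|---|---|---|---|
| 2% | 93.2% | 91.9% | 96.7% |
| 3% | 93.8% | 92.8% | 95.5% |
| 5% | 92.6% | 91.3% | 95.1% |
| 7% | 95.0% | 93.7% | 95.4% |
| 10% | 93.8% | 92.6% | 95.0% |
| 11.2% | 93.9% | 92.4% | 94.6% |

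*Logit link, robust standard error, exact interval when there are no events. The gap between the first two columns, 1.0 to 1.5 points, is the part due to clustering.

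**The case against.** The strongest reply is that SAP 5.2.2 is a general-methods section and that the endpoint-specific text, Section 6.3, is not in the public copy. SAP 6.2 restates its own interval method, so 6.3 may do the same and may name a different one. This stands as a limit on certainty. But 5.2.2 names this endpoint and its interval explicitly, and nothing visible overrides it. No fault is claimed on the unit or display, which 6.3 may already settle.

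Second, the SAP gives no formula, so the plain Wald form is my reading. A continuity-corrected form is also a normal approximation and does better. Over 2–11% it averages 93.8% at n = 100 (minimum 86.6%, below 95% at 62% of rates) and 94.5% at n = 160. Most of the average shortfall would go; the poor coverage at low rates would not. No correction is mentioned.

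Third, the size depends on an assumed range. The interval around the cited success rate, 83.1% to 92.7%, implies failure rates of 7.3% to 16.9%, and it comes from a different device. Over that higher range the planned interval averages 93.3% at n = 100, so the shortfall is under 2 points. It shrinks but does not vanish, and since clinic returns are only part of failures, lower rates remain plausible. The 80% is a minimum at one rate and should not be read as typical.

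Fourth, Wilson also dips below 95% at a good share of rates. That is true, so mean coverage and the balance of misses are the fairer comparison.

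Finally, the endpoint is descriptive and counts will be shown beside the proportion, so few readers would be misled by a 0% to 0% interval. That limits the weight of the point but is not a reason to keep the method.

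**Conclusion.** The concern holds, as a minor correction. By visit, with 100 to 160 women and a true return rate of 2% to 11%, the planned interval averages 91% to 92% coverage instead of 95%, and nearly all the misses leave the true rate above the upper limit. It can also print an impossible negative limit or a zero-width interval. This rests on the assumed rate range, on reading the method as plain Wald, and on the by-visit reading of the visible text. Restricting the range to 5% to 11% still gives a mean of 92% at n = 100.

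The pooled result, 91% to 94% for the planned interval against 95% to 97% for the GEE, applies only if such a figure is reported and if the borrowed ICC is about right.

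SAP 5.1 makes all analyses descriptive, and this endpoint is neither the primary nor the named secondary, so no decision rule or sample size changes. The continuation rate, which shares the method in 5.2.2, is much less affected: with 160 women the same interval covers 93.6% to 95.0% at continuation rates of 62.5%, 70%, 75% and 80%.

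**What to change.** In SAP 5.2.2, for the clinic-return proportion:

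1. For by-visit figures, replace the normal approximation with a Wilson or exact (Clopper–Pearson) interval, and name which.
2. For any figure pooled over visits, use the intercept-only logit GEE clustered on subject from SAP 6.1, and report the number of injections as well as the number of women. If no returns are seen, use an exact interval.

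On the zero case, an exact upper limit on 300 injections is 1.2% but treats injections as independent. Counting the 100 women instead gives 3.6%, which is cautious and needs no such assumption.

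The cost is one or two sentences. The same GEE is already planned for the primary endpoint, and no data collection, sample size or primary analysis changes. The downsides are a second interval method in the SAP, a slightly wider pooled interval, and some conservatism if the exact interval is chosen (mean coverage 97% at n = 100).
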